5.2.5 Rescue Medication for Breakthrough Infections

Subjects in Part C will be prescribed an approved regimen for curative therapy for malaria, to assure final parasite clearance, at recrudescence or at the end of the trial. All subjects will receive Riamet; in addition, Primacin 45 mg will be administered to those subjects who have evidence of gametocytemia. *P. falciparum* 3D7, the parasite strain constituting the inoculum, is fully sensitive to both Riamet and Primacin. Loss of sensitivity is regularly checked in vitro.

The curative/rescue drugs will be inventoried prior to the beginning of trial enrollment on trial accountability logs, to document condition upon receipt, including lot numbers. The Investigator or qualified trial personnel designated by the Investigator will ensure that the received drugs are the specified formulation. The trial site Pharmacist or a nominee designated by the Investigator is

responsible for maintaining an accurate inventory and accountability record of drug supplies for this trial.

- Riamet (20 mg artemether and 120 mg lumefantrine) oral tablets. A course of treatment comprises 6 doses of 4 tablets each (total course of 24 tablets) given over a period of 60 hours. Four oral tablets are administered as a single-dose, administered twice daily at 12 hour intervals, ie, time 0, 12 hours, 24 hours, 36 hours, 48 hours, and 60 hours. Each dose of tablets administered orally should be consumed with food
- Primacin (7.5 mg primaquine phosphate) oral tablets: To clear gametocytes of *P. falciparum*, subjects will receive 45 mg as a single dose with food at the end of their Riamet treatment if gametocytes are identified by gametocyte-specific PCR.

Compulsory commencement of clearance medication will occur no later than 21 days after the last dose of M5717. Administration of rescue medications prior to Day 22 will be determined at the Investigator's discretion using the following criteria:

- Failure of clearance: defined as failure to clear parasitemia by at least 10-fold at 72 hours post IMP administration
- Recrudescence: defined as ≥ 5000 blood stage parasites/mL and a 2-fold parasitemia increase within 48 hours, or re-occurrence of malaria symptoms with a malaria clinical score > 6 .

Early intervention can occur if either poor responses or fast responses are seen following M5717 treatment. This flexibility is designed to ensure subject safety and to avoid subject inconvenience if useful data cannot be obtained. However, pre-emptive rescue treatment can commence whenever deemed necessary by the Investigator.

Subjects will be monitored, either in the trial site, or by telephone for 3 days to ensure adherence to the rescue medication therapy. In any case, safety assessments should be performed prior to administration of the rescue medication and recorded in the eCRF.

Blood and urine samples will be collected for safety evaluation (hematology, biochemistry, coagulation, urinalysis, and CCI) as will blood samples for PK throughout the residential and ambulant period (at time points indicated in Table 3). This will include hematology, biochemistry, ECG, vital signs, physical examination, coagulation profile and urinalysis. However, serology, red blood cell auto-antibodies, and serum storage collection will still be collected at Day 22 regardless of the study day that rescue medications are administered.

CCI

CCI

CCI

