- t Riamet and Primacin. If rescue medications are required prior to Day 22, safety assessments must be performed pre administration of Riamet. This assessment will include hematology, biochemistry, ECG, vital signs, physical examination, coagulation profile, and urinalysis. However, red blood cell auto-antibodies, and serum storage collection will still be collected at Day 22 regardless of the trial day that rescue medications are administered. Administration of rescue medications prior to Day 22 will be determined at the Investigators discretion using the following criteria:
- Failure of clearance: defined as failure to clear parasitemia by at least 10-fold at 72 hours post IMP administration
 - Recrudescence: defined as ≥ 5000 blood stage parasites/mL and a 2-fold parasitemia increase within 48 hours, or re-occurrence of malaria symptoms with a malaria clinical score > 6 .
- u Subject will be contacted daily via phone calls while outpatient, from Inoculum Day 2 to Inoculum Day 4, as well as on Day 23 to Day 25, for a safety check and compliance of rescue medication use.
- v Serum samples will be collected at Inoculum Day 1 (pre inoculation), Day 22 (pre Riamet treatment) and the End of Trial visit (Day 44 [± 2 days]). These samples will be stored and will be used only in case any safety concerns arise and additional safety parameter testing is required.
- Time window: Samples and assessments obtained within the allowed time window from dosing will not be captured as a protocol deviation, as long as the exact time of the assessment/sample collection is noted on the source document and data collection tool (eg, eCRF).

Table 4 Allowed Time Windows

Time Point	Tolerance Window
Pharmacokinetic CCI (blood samples)	
Predose	- 60 min to 0 h
0.5 h to 1.5 h post	± 3 min
2 h post	± 3 min
4 h to 20 h post	± 5 min
24 h to 72 h post	± 10 min
84 h to 144 h post	± 2 h
192 h to 384 h post	± 6 h
504 h post	± 24 h
768 h post	± 48 h
1032 h post	± 48 h
12-Lead Electrocardiogram/Vital Signs/Respiratory Rate/Temperature/Safety Laboratory Samples	
Predose	- 90 min to 0 h
0.5 h to 1.5 h post	± 10 min
2 h post	± 10 min
4 h to 20 h post	± 10 min
24 h to 72 h post	± 20 min
84 h to 144 h post	± 2 h
192 h to 384 h post	± 6 h
504 h post	± 24 h
768 h post	± 48 h
1032 h post	± 48 h
Blood Pressure Measurements	
Day 1	± 60 min

2 Sponsor, Investigators and Trial Administrative Structure

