Part C is a single-center, open-label trial using the *P. falciparum* IBSM human challenge to assess the antimalarial activity of M5717 in healthy subjects infected with malaria under controlled conditions. The trial is planned to be conducted in up to 3 cohorts (n=8 per cohort). CCI

The following options may be considered:

[figure not shown]
- If the initial dose leads to a complete reduction of parasitemia and does not lead to observed recrudescence in any subjects, then a lower dose will be used for the second cohort
- If recrudescence is observed in an insufficient number of subjects, so that the MIC cannot be derived, then a second cohort with a lower dose should be initiated
- If recrudescence is observed in enough subjects so that the MIC can be derived, then the need for a higher dose will be evaluated and decided by the SMC.

CCI

Figure 6 presents an illustration of the time schedule for Part C.

Figure 6 Illustration of Time Schedule for Challenge Model

In D1 to In D9 = Day of Inoculum administration (In D1) to 9 days post administration of the Inoculum (In D9); IMP = investigational medicinal product; IV = intravenous.

This example assumes that the IMP is administered on Inoculum Day 9.

In order to be able to observe the MIC and model the MPC, one needs to assess the drug concentration at the time that parasite count is at its lowest level. This implies that the lowest parasite count must be observed. Provided that a high enough dose is administered, the MIC should be reached after the subject has recovered from any clinical symptoms of malaria, and when parasite densities have fallen below the level of microscopic detection, as the sensitivity of microscopy is only 50/ μ L (approximately 10^8 parasites total). Sensitive qPCR methods now allow timely (assay time approximately 4 hours) detection of very low parasitic densities (below 100 parasites/mL, which represents sensitivity up to 1,000 times greater than thick blood smears by microscopy), so it is possible to follow the sub-latent parasitemia levels as they decline and then rise again. Once there is clear evidence by real-time qPCR that parasitemia is rising (parasitemia of $\geq 5,000$ asexual blood stage parasites and increasing 2-fold within 48 hours), rescue medication will be administered at the decision/discretion of the Investigator. The subject will thus be cured of their infection before or at emergence of advanced clinical symptoms of malaria infection.

CCI

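### Protocol Section 5.2.5 allows early rescue for undefined fast responses, outside its own two criteria, and the visible plan gives no analysis status to a subject rescued without recrudescence

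*Protocol*

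**What the plan says.** Protocol Section 5.2.5 introduces early rescue with "Administration of rescue medications prior to Day 22 will be determined at the Investigator's discretion using the following criteria" and lists two items. The first is "Failure of clearance: defined as failure to clear parasitemia by at least 10-fold at 72 hours post IMP administration". The second begins "Recrudescence: defined as ≥ 5000 blood stage parasites/mL and a 2-fold parasitemia increase within 48 hours" and has an alternative: returning symptoms with a malaria clinical score above 6. Table 3 footnote t repeats both items. Clearance medication becomes compulsory no later than 21 days after the last dose, which is Day 22 for a single dose.

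The same section then states: "Early intervention can occur if either poor responses or fast responses are seen following M5717 treatment". The reason follows: "This flexibility is designed to ensure subject safety and to avoid subject inconvenience if useful data cannot be obtained". A separate sentence lets the Investigator start pre-emptive rescue whenever it is thought necessary.

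Protocol Section 5.2.4 explains that MIC and MPC need the drug concentration at the lowest parasite count, and adds: "This implies that the lowest parasite count must be observed". It describes following parasitemia by qPCR as it falls and rises again. After qPCR has been negative for 48 hours, sampling continues about three times a week, at the Investigator's discretion, until Day 22.

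The number and percentage of subjects with recrudescence is a secondary endpoint (SAP Section 5). Protocol Section 8.5.2.3 defines recrudescence statistically as a rise of more than 1 log10 over two or more consecutive qPCR results, after the initial fall. SAP Section 12.2 lists rescue medication by subject and day.

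**The concern.** A poor response corresponds to the first listed criterion. A fast response corresponds to neither, and nothing in the visible text says how fast is fast. It also fits neither of the two occasions for curative therapy named at the start of Section 5.2.5: recrudescence or the end of the trial.

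A subject who has cleared quickly and not yet regrown is one in whom the nadir and any regrowth may still have to be seen. Rescue is curative, so observation under M5717 alone ends when it starts, although visits and samples continue to Day 44. If such a subject is then tabulated as having no recrudescence, the endpoint mixes absence of regrowth with absence of the opportunity to regrow. Faster clearance at higher doses could make this more common there, which would blur the comparison of recrudescence between doses.

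**Working it through.** The documents give no figure to reproduce: Part C uses 8 subjects per cohort by precedent (Protocol Section 8.1). The check compares passages, then uses labelled illustrations.

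**1. Grounds for rescue before Day 22**
- Failure of clearance: in Section 5.2.5 and in Table 3 footnote t.
- Recrudescence (count or clinical score): in both.
- Pre-emptive, when judged necessary: in the later text of Section 5.2.5 only.
- Fast response: in the later text of Section 5.2.5 only, undefined.

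**2. Status of a subject rescued without recrudescence**
- Protocol Section 8.5.2.3 defines the event but not what happens when rescue comes first.
- Protocol Section 8.5.1 takes no action on missing data. Its rule for withdrawn subjects does not apply, because a rescued subject stays in the trial.
- SAP Section 8.2 keeps any subject with evaluable postdose PD data in the PD Analysis Set, unless a clinically important deviation or event affecting PD excludes the subject.
- SAP Section 9 bases proportions on the number of subjects in the analysis set. That paragraph is headed for demographics, baseline and safety, but no different rule is visible for PD.
- SAP Section 12.2 only lists rescue.

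On the natural reading the subject stays in the denominator as a non-event.

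**3. Effect on one cohort of 8**

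Let r be the observed recrudescences and k the subjects rescued early without recrudescence.
- Counted as non-events: r/8.
- Bounds, treating none or all of the k as recrudescent: r/8 to (r + k)/8, so each such subject widens the range by 1/8 = 12.5 percentage points.
- Example (assumed r = 2, k = 2): non-events give 2/8 = 25%; the bounds are 25% to 50%. If both rescues precede both events, Kaplan-Meier gives 1 − (5/6)(4/5) = 33%.
- Dropping these subjects as not evaluable is no remedy. If 4 recrudesce and the 4 rescued would never have done so, the true 4/8 becomes 4/4.

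**4. Loss of information** (binomial; the recrudescence rate, the numbers still followed and the threshold of 3 are all assumptions)

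At a true rate of 50%, the chance of seeing at least 3 recrudescences is 86% with 8 subjects followed to Day 22, 66% with 6 and 31% with 4. At 25% it is 32%, 17% and 5%.

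**5. How much regrowth time is at stake**

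Net regrowth needs concentrations below the MIC (predicted 3 ng/mL), not merely below the MPC (10 ng/mL). Assume exactly 10 ng/mL at 192 h, the 8-day target for cohort 1, and single-exponential decline. The time to reach 3 ng/mL is 192 + t½ × log2(10/3) = 192 + 1.737 × t½.
- Predicted median half-life 257 h: 192 + 446 = about 638 h, after compulsory rescue at 504 h.
- Predicted 20th percentile 127 h: 192 + 221 = about 413 h, leaving 91 h, or about 4 days.
- Break-even: (504 − 192)/1.737 = about 180 h.

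These are preclinical predictions. The observed half-life is not given, so the loss cannot be fixed from the documents.

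**6. PRR**

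Protocol Section 8.5.2.3 fits the decay only up to the first time point at which all replicates are undetected. Rescue after that point does not change it.

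**The case against.** The strongest reply is that this is a discretionary permission, tied to safety and to cases where useful data cannot be obtained. On its own terms it should not touch a subject whose nadir or regrowth is still obtainable, and the two listed criteria are themselves applied at the Investigator's discretion. Step 5 gives this some support: with a long half-life, waiting to Day 22 might yield no regrowth. What remains is that the qualifier has no test attached, fast is undefined, and the sampling plan keeps cleared subjects under observation to Day 22. The separate sentence on pre-emptive rescue already covers safety, and this point leaves it untouched.

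It is also fair that PD methods and PK/PD modelling are deferred to separate documents (SAP Sections 16.2.1 and 16.2.3) and that parts of the protocol are redacted. A rule for rescued subjects may exist there; the gap is in the visible plan only.

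A reader might infer more: that quick clearance removes regrowth by rule, that every clearer becomes eligible by Day 9, and that 13 of 21 days (62%) of regrowth observation are lost. The documents do not support this. The permission is optional, no passage sets rescue at Day 9, and the 13-day figure treats the MPC as the regrowth threshold. Nor must next-dose decisions wait for regrowth to Day 22: Protocol Section 5.2.8 lets the SMC decide on PK/PD data up to at least Day 9.

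**Conclusion.** The inconsistency is real. Two places list two criteria, and the later text of Section 5.2.5 adds an undefined third ground that sits uneasily with the follow-up described in Section 5.2.4. If it is used, the recrudescence percentage can be understated and there is less information on MIC and MPC. PRR is largely unaffected. The size cannot be derived: it depends on how often the permission is used and on the observed half-life. The only firm figure is that each subject rescued without recrudescence leaves 12.5 percentage points undetermined in a full cohort of 8; the other percentages above rest on assumed rates.

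This reading takes early intervention to mean rescue, as the section title and the sentence on pre-emptive rescue imply, and takes the visible text as the whole plan for these subjects. Which clinical rule is right is outside this review.

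**What to change.** - Reconcile the criteria list in Protocol Section 5.2.5, its later paragraph and Table 3 footnote t so that they state one consistent set of grounds for rescue before Day 22. The sponsor and investigator decide what that set is.
- Record the ground for each early rescue in the eCRF: safety, failure of clearance, recrudescence, or other.
- In the SAP or the separate PD plan, censor at rescue any subject rescued before Day 22 without meeting the Section 8.5.2.3 definition. Estimate time to recrudescence by Kaplan-Meier, report the number of such subjects by ground, and give bounds treating all or none of them as recrudescent. Do not report them as having no recrudescence or as cured. The bounds are needed because rescue prompted by a fast response is unlikely to be independent of later recrudescence.

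The cost is protocol wording, one eCRF field and slightly more analysis. The recrudescence estimate will be less precise, which with 8 subjects per cohort will be noticeable.

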5.2.8 Safety Monitoring Committee and Decision Criteria

The SMC will be set up as described in the SMC charter.

The SMC will determine:

- Dose escalation/de-escalation
- Termination of further dose escalation in Part A if it is expected that further escalation will not be tolerated or if it is determined that a maximum exposure may be reached (Section 5.5.3)
- The need to start a multiple dosing regimen in Part B
- The timing to start Part C
- The respective dose(s) and dose escalations to be evaluated in Part B and Part C
- Request unblinding of data, if deemed necessary
- Suspension of enrollment, trial modification, or trial termination.

Part A and Part B

The SMC will regularly meet at approximately Day 25 after all subjects in a given SAD/MAD cohort have received administration of M5717 or matching placebo. A medical monitoring report summarizing all safety and tolerability data (AEs, safety laboratory data, ECG, and vital signs) collected from minimally 6 subjects up to and including Day 11 (around 1 median half-life) for SAD cohorts will be provided to the SMC for review. The medical monitoring report may also include a summary of the safety data for all previous dose cohorts, when appropriate. The first 2 SMC meetings in the SAD part (Part A) will also contain PK data from 6 subjects up to 144 hours postdose. For later SMC meetings, PK data of the preceding cohort(s) will be reviewed as applicable to support the safety and tolerability assessment, as deemed necessary by the SMC. Safety laboratory and PK data included in the monitoring report to be provided to the SMC will undergo quality control by the respective laboratory(ies) responsible for this data.

In addition, the SMC can modify PK sampling times and/or ECG recording times based on new information received (eg, to better align with timing of t_{max}) but is not allowed to increase the number of PK sampling points unless by amending the clinical trial protocol.

CCI

In case of a safety concern, the SMC members are allowed to request immediate unblinding of the data. In the pivotal toxicology studies, vomiting and diarrhea were identified as dose-limiting events, so these events will be carefully monitored. The SMC may also request access to unblinded PK data in case the need arises, to evaluate the correlation between exposure and safety data reviewed by the SMC.

Once the SMC has defined a dose, based on safety data, that does not allow further escalation of the dose, the SMC may recommend testing lower doses according to the same Schedule of Assessments as for the other cohorts, if this is deemed necessary to better characterize the safety and/or PK profile of M5717 prior to termination of Part A.

Part C

The SMC will review all available safety (up to at least Day 11) and PK/PD data (up to at least Day 9) after subjects of each cohort have been treated and will decide whether an additional cohort needs to be included, as well as the dose to be investigated in that cohort. In principle, a maximum of 3 doses are foreseen to accurately describe the PK/PD correlation. In addition, the SMC may modify PCR sampling times and the number of samples based on new information received (eg, to better align with timing of the PRR).

5.2.9 Justification for Dose

In reference to its mode of action, the selectivity of the eEF2 target for Plasmodium and the availability of data from a relevant animal species model for predicting human responses, M5717 was not classified as a high-risk molecule and the NOAEL approach was applied to support the starting dose.

The starting dose for the first human use of M5717 was determined based on the following factors which are detailed in the following sections:

- Identification of a MRSD, using the NOAEL identified in pivotal GLP toxicology studies in the most sensitive species, as recommended by the FDA Guidance Estimating the Maximum

Safe Starting Dose in Initial Clinical Trials for Therapeutics in Adult Healthy Volunteers 2005
(7)

- Consideration of NOAEL exposures reached in animal toxicity studies
- PK/PD modeling of preclinical data for the purpose of predicting the ED range in humans.

In the 14-day toxicology trial in dogs, M5717 was administered orally 2 times for a period of 3 days with 2 days in between, followed by 4 days of treatment. In the 14-day toxicology trial in rats, M5717 was administered orally 2 times for a period of 3 days, with 6 days in between. An extensive summary of all toxicology findings is given in the IB. The main observations are summarized in Table 5 along with the plan how to adequately monitor these potential findings.

CCI

CCI

CCI

CCI

CCI

and glomerular podocytes occurs frequently, with the development of the renal toxicities of aminoglycosides and chloroquine, respectively.

CCI

CCI

CCI

CCI

CCI

CCI

CCI

CCI

CCI

CCI

5.2.10 Inclusion of Special Populations

Not applicable.

5.2.11 Rationale for Endpoints

Standard safety, tolerability and PK of M5717 will be determined using the following parameters:

- Nature, incidence, and severity of AEs/SAEs, including relationship to trial treatment, AEs/SAEs leading to dose modification or discontinuation of trial treatment
- Safety laboratory parameters (hematology, coagulation, biochemistry [specifically ALT and AST], urinalysis, and CCI)

CCI

- Vital signs (body temperature, BP, heart rate), respiratory rate, and 12-lead ECG. The digital 12-lead ECG will be used for concentration QTc analysis
- Blood concentrations of M5717 will be used to determine the standard PK parameters in each trial part
- PRR, PCT, and MIC are validated endpoints for PK/PD analysis of malaria compounds

CCI

5.3 Selection of Trial Population

Only persons meeting all inclusion criteria and none of the exclusion criteria may be enrolled into the trial as subjects. Prior to performing any trial assessments not part of the subject's routine medical care, the Investigator will ensure that the subject has provided written informed consent following the procedure described in Section 9.2.

Inclusion and exclusion criteria are to be checked at Screening and Day -1/ Day -2 of Part A and Part B unless otherwise stated.

For Part C the criteria have to be checked at Screening, prior to inoculation and again prior to IMP administration.

5.3.1 Inclusion Criteria

1. Adult men and WNCBP, 18 to 55 years of age (inclusive), with total body weight ≥ 50.0 kg and body mass index (BMI) between 19.0 kg/m^2 and 29.9 kg/m^2 (inclusive).
2. A female subject is eligible to participate if she is not breastfeeding and not a woman of childbearing potential (WOCBP as defined in [Appendix I](#)) confirmed at Screening by fulfilling one of the following criteria:
 - a. Postmenopausal defined as having amenorrhea for ≥ 12 consecutive months following cessation of all exogenous hormonal treatments, and increased follicle-stimulating hormone (FSH) $> 40 \text{ mIU/mL}$.
 - b. Documentation of irreversible surgical sterilization by hysterectomy, bilateral oophorectomy, or bilateral salpingectomy. Tubal ligation alone is not sufficient.
3. A male participant must agree to use a condom with or without spermicide during sexual activity with a female partner of childbearing potential and to have their female partner use a highly effective contraception (ie, methods with a failure rate of less than 1 % per year) as detailed in [Appendix I](#) of this protocol, during the treatment period and for at least 20 weeks after the last dose of IMP administration and to refrain from donating sperm during this period.
4. Healthy as assessed by the Investigator with no clinically significant abnormality identified on physical examination or laboratory evaluation and no active clinically significant disorder, condition, infection or disease that would pose a risk to subject safety or interfere with the trial evaluation, procedures, or completion.

5. Stable nonsmokers for at least 6 months preceding Screening.
6. Able and willing to comply with restrictions on exposure to sunlight and to give written informed consent.
7. Part C additional: Do not live alone (from start of malaria inoculation until at least the end of the antimalarial drug treatment), willing to provide contact details of a person living with them, and be contactable and available for the duration of the trial; no history of possible malaria exposure.

